10.4.2 ANALYSIS OF THE PRIMARY EFFICACY ENDPOINT(S)

As noted above, this is a phase 2 pilot trial. However, expansion to a phase II trial will depend on demonstration of CR/CRi amongst 4 of the initial 10 treated patients. For illustration only, we have provided Simon Two-Stage Calculation, using power of 90% and Type I error rate of 0.1.

N1	R1	PET	N	R	Ave N	Alpha	Beta
10	3	0.514	19	9	14.38	0.084	0.095

Currently, we see approximately 50 new ALL patients per year, with around 70 in active followup. Given this, we can anticipate enrollment of the first 6 patients over a 12 month interval.

10.4.3 ANALYSIS OF THE SECONDARY ENDPOINT(S)

- Minimal Residual Disease (MRD) will be studied as a dichotomous endpoint using a cutoff of 1×10^{-4} cells/transcripts as the lower limit for residual leukemia, and presented as the percentage of patients reaching this landmark as their best response. MRD assessment will be obtained with each bone marrow biopsy assessment, as described below.
- Progression Free Survival and Overall Survival will be reported as per Cheson and Lugano Criteria, and analyzed using a standard Kaplan-Meier approach. Patients will undergo bone marrow biopsy evaluation after each cycle of therapy per standard of care to facilitated assessment. Patients achieving CR/CRi at the end of consolidation with marrow involvement will have follow-up bone marrow biopsy evaluation every 3 months in the first year following their last cycle of therapy, and every 6 months in the subsequent 2 years following their last cycle. Patients who remain in remission greater than 3 years from their last cycle of therapy will have bone marrow biopsy evaluation performed as needed. Patients without marrow involvement will have follow-up imaging (CT or PET/CT) every 3 months in the first year following their last cycle of therapy, and every 6 months in the subsequent 2 years following their last cycle. Patients progressing to allogeneic transplant following therapy will be censored at the time of conditioning.
- Safety will be continually assessed during the course of induction and consolidation cycles. Safety assessment will continue at a minimum of every 3 months for those who do not progress to allogeneic transplant or alternative therapy.

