4.2.2 SECONDARY ENDPOINTS

Secondary Endpoints will include

- 1) Evaluation of safety of CPX-351 using CTCAE 5.0.
- 2) Minimal residual disease assessment (MRD) by 10 color flow cytometry and next generation sequencing (NGS) by Clonoseq (for Philadelphia negative leukemia) or PCR for BCR-ABL (for Philadelphia positive leukemia) at day 28. Using a threshold of 0.01% leukemic cells, MRD provides a better estimate leukemic cell sensitivity to therapy, and correlates with both PFS and OS.
- 3) Progression Free Survival as defined by Cheson and Lugano Criteria (ref 27 and 32), namely progression, failure to respond, or death, as assessed from time of first treatment. The 12 month progression free survival rate with standard chemotherapeutic approaches in relapsed ALL is estimated at 10%. PFS is a standard estimate that accounts for response rate, response duration, and mortality to estimate therapeutic benefit in clinical trials.
- 4) Overall Survival as defined by Cheson and Lugano Criteria (ref 27 and 32), namely death due to any cause as assessed from time of first treatment. The 12 month overall survival for those with standard chemotherapeutic approaches in relapsed ALL estimated at 20%. Overall survival is a standard criteria for assessing therapeutic benefit in clinical trials.

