6.1.9 DURATION OF THERAPY

All patients completing induction will be evaluable for efficacy. Consolidation may be started at the time of hematologic recovery (28-75 days after start of induction) for those achieving a complete remission or complete remission with incomplete hematologic recovery. Consolidation cycles may be repeated at the time of hematologic recovery for a maximum total of 3 consolidation cycles.

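### MRD negativity is defined at day 28 in section 4.2.2 but analysed as best response over every marrow in section 10.4.3, so the reported rate can exceed the defined endpoint

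*Combined protocol and SAP*

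**What the plan says.** Section 4.2.2 lists the MRD assays by Philadelphia status and ends the list with "PCR for BCR-ABL (for Philadelphia positive leukemia) at day 28"; I take the day to govern the whole list. The next sentence, opening "Using a threshold of 0.01% leukemic cells", gives the purpose: MRD is meant to show how sensitive the leukaemia is to therapy, and it is said to track PFS and OS.

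Section 10.4.3 makes MRD a yes/no endpoint at 1×10^-4, to be "presented as the percentage of patients reaching this landmark as their best response". It continues: "MRD assessment will be obtained with each bone marrow biopsy assessment, as described below". The marrow schedule it points to is in the next bullet, on PFS and OS: "Patients will undergo bone marrow biopsy evaluation after each cycle of therapy per standard of care". For patients with marrow involvement who are in CR/CRi at the end of consolidation, that bullet adds marrows every 3 months for a year and every 6 months for two more years. Section 6.1.9 allows consolidation "for a maximum total of 3 consolidation cycles". Section 7.1.13 instead leaves marrows during follow-up to the investigator.

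The study summary, section 3 and section 10.2 list MRD without a time point.

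**The concern.** The analysis rule does not estimate the endpoint that section 4.2.2 defines. Two analysts, each following one section, could report different MRD rates from the same data, and nothing in the plan says which is the secondary endpoint.

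The difference can go only one way. A patient's best result over several marrows cannot be worse than the day-28 result. The number of marrows also follows from how the patient does: those who respond or are judged to benefit go on to consolidation and are sampled again, while those who do not usually have one scheduled sample after baseline. A best-ever rate therefore depends partly on time on study. That weakens its use as a post-induction sensitivity measure, and any association with PFS or OS would be partly built in, because patients who stay progression-free longer have more chances to test negative.

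Sections 10.2 and 10.4.11 say the endpoints may support an expansion or a later study, so a reader of the results needs to know which quantity is being reported.

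**Working it through.** **The plan's own figures.** The plan gives no target rate, sample size, power or interval for MRD. Its only design calculation is the illustrative Simon table in section 10.4.2, for CR/CRi. With 35% against 65%, n1 = 10, r1 = 3, N = 19 and r = 9, the exact binomial gives PET 0.5138, average N = 10 + (1 − 0.5138) × 9 = 14.38, alpha 0.0844 and beta 0.0952. These match the table. MRD does not enter it.

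**Threshold.** 0.01% = 0.0001 = 1×10^-4. The cutoff is the same in both sections; only the timing rule differs. The landmark in section 10.4.3 refers back to the cutoff, the only antecedent in its sentence, and not to a date.

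**Marrows per patient after baseline.**
- Stops after induction: 1.
- Induction plus three consolidations: 1 + 3 = 4.
- Full follow-up schedule of section 10.4.3: months 3, 6, 9, 12 (4) and 18, 24, 30, 36 (4) after the last cycle, so 4 + 8 = 12.
- Within the 30-month participant duration in the study summary, counted from induction day 1 (my assumption): at the 28-day minimum intervals in section 7.3.2, the third consolidation starts at 3 × 28 = 84 days, about month 2.8. The 24-month follow-up marrow falls at about month 26.8 and the 30-month one at about 32.8, so six follow-up marrows fit: 4 + 6 = 10. The 35-day minimum in the schedule of events gives the same count (105 days, about month 3.5). At the longest intervals, 75 + 56 + 56 = 187 days, about month 6.1, the 24-month marrow falls at the boundary. Hence about 10.

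**Direction and smallest step.** Best of k ≥ day-28 result for every patient, so the best-response rate ≥ the day-28 rate. With 10 patients, one first negative after day 28 adds 1/10 = 10 percentage points.

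**Illustration.** Let p be the day-28 negative rate, f the share of day-28-positive patients who go on to k marrows, and c the chance per later marrow of a first negative. The documents give none of these. Then

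best-response rate = p + (1 − p) × f × [1 − (1 − c)^(k−1)].

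With p = 0.30 and k = 4:

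| f | c | Calculation | Rate |
|---|---|---|---|
| any | 0 | 0.30 + 0 | 30% |
| 0.3 | 0.05 | 0.30 + 0.70 × 0.3 × (1 − 0.95^3) = 0.30 + 0.21 × 0.1426 | 33% |
| 0.5 | 0.20 | 0.30 + 0.70 × 0.5 × (1 − 0.80^3) = 0.30 + 0.35 × 0.488 | 47% |

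**The case against.** The strongest reply is that best MRD is a legitimate quantity. The study summary states the objective as MRD burden after treatment with CPX-351, and treatment includes consolidation. A patient who first clears MRD during consolidation may show a real drug effect. This stands. A reader might infer that the section 10.4.3 rate is simply inflated or biased; the documents do not support that. It is a different estimand from the one in section 4.2.2, and the two coincide if nobody converts after day 28.

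A reader might also infer that the rule credits CPX-351 with clearance achieved by later therapy. The documents limit this. Section 5.4.1 ends the follow-up rules once a patient starts non-study cancer treatment, and section 7.6 bars other anti-cancer treatment during the treatment phase. What remains is narrower: the only explicit transplant cut-off, censoring at conditioning, is in the PFS/OS bullet and is not stated for MRD.

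Two numerical readings also go too far. Twelve marrows need three years of follow-up after the last cycle, which does not fit in 30 months. And if one assumes that a persistently positive patient has an isolated negative 5%, 10% or 20% of the time, independently, four looks give 1 − (1 − q)^4 = 19%, 34% or 59%. Those figures describe only such a patient with all four marrows and are not the trial's MRD rate; the documents supply no such error rates.

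Finally, the stakes are modest. All endpoints are exploratory, and expansion rests on CR/CRi alone. With n = 10, sampling error is large: the exact 95% interval is 6.7–65.2% for 3/10 and 12.2–73.8% for 4/10. This lowers the priority but does not remove the conflict.

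**Conclusion.** The inconsistency is real and should be corrected before analysis. Sections 4.2.2 and 10.4.3 share a threshold but not a time point, and following section 10.4.3 gives a rate equal to or above the defined endpoint, from a number of marrows that depends on outcome.

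The direction is certain by construction; the size is not known. One late conversion in 10 patients is worth 10 percentage points. The 33–47% range against 30% at day 28 rests on assumed values: a 30% day-28 rate, 30–50% of day-28-positive patients reaching four marrows, and a 5–20% chance of a first negative at each later one. No hypothesis test, error rate, sample size or expansion decision changes. The consequence is confined to what the reported MRD figure means.

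**What to change.** In section 10.4.3:

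1. Make MRD below 1×10^-4 at the day-28 induction assessment the secondary endpoint, matching section 4.2.2.
2. State the denominator as efficacy-evaluable patients with marrow disease, and count a missing day-28 result as not negative. The restriction is needed because section 7.1.13 requires no day-28 marrow when extramedullary disease is confirmed and the pre-study marrow is negative.
3. Report best MRD on protocol therapy as a separately labelled supplementary line. Count only samples taken before transplant conditioning or other anti-leukaemia therapy, and give the number of assessments per patient.

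This is a wording change that uses samples already planned. The cost is that the headline MRD rate may be less favourable. Making the change before the MRD data are analysed also prevents a choice between the two rules after the results are known.

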10.4.4 SAFETY ANALYSES

Using summary statistics, safety data will be coded using CTCAE 5.0 criteria, with each AE being counted only once for a given participant. The severity, frequency, duration, outcome, and relationship of AEs to study agent, as defined by the treating investigator, will be presented by System Organ Class (SOC) and preferred term groupings. Adverse events leading to premature discontinuation from the study drug, adverse events of special interest, and serious treatment-emergent AEs will be presented in a table.

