6.1.7 STARTING DOSE AND DOSE ESCALATION SCHEDULE

Patients will receive induction with CPX-351 at a dose of 100 u/m² administered intravenously over 90 minutes on days 1, 3 and 5 of a 28 day cycle.

This may be followed by consolidation with CPX-351 at a dose of 65 u/m² administered intravenously over 90 minutes on days 1 and 3 of a 28 day cycle.

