7.3.7 SCHEDULE OF EVENTS TABLE

Procedures: Day:	Screening^a	1	2	3	4	5	6	7	10	28	29+ⁱ	End of Treatment/ Early Term.^g	Follow- Up
Informed consent	X												
Demographics and Medical History	X												
Baseline Symptoms ^b		X											
day Performance Status	X												
Concomitant Medication Review	X	Assess throughout Induction and Consolidation											
Review Adverse Events ^c		Assess throughout Induction and Consolidation										X	
CPX-351 Administration ^d		X		X		X							
Physical Examination	X												
Serum pregnancy test ^e	X												
Vital signs (temp, pulse, resp, BP, weight)	X	X		X		X						Per SOC	
Height	X												
12-lead EKG	X												
Echocardiography/MUGA	X										X ^l		
CBC with differential	X	X	X	X	X	X	X	X	X	X	X	Per SOC	
Serum chemistry testing ^f	X	X	X	X	X	X	X	X	X	X	X	Per SOC	
LDH, uric acid, magnesium, phosphorus	X	X	X	X	X	X	X	X				As needed	
Coagulation studies (PT/INR, aPTT, fibrinogen)	X												
Urinalysis with microscopy	X												
Bone marrow biopsy ^k	X										X		
CT or PET/CT Scan ^m	X										X		
Correlative studies ⁿ	X ^{1,2,3}										X ³		
CSF for ALL involvement/IT chemo ^j	X								X				
Follow-Up													X

- a. Screening assessments will be performed within 28 days of the dose of study drug Day 1. Any standard of care procedure performed within 28 days of Day 1, may be used for screening/eligibility even if performed prior to consent.
- b. Baseline symptoms are defined as those present at the closest time before the start of study drug administration.
- c. Adverse event data will be captured from the time of consent until 30 days after the last dose of CPX-351.

- d. CPX-351 induction therapy will only be administered to a subject following hospital admission. One induction will be administered. Patients with a CR, CRi, PR or determined by the PI to be experiencing clinical benefit after induction, may receive up to 3 consolidation treatments, all administered as an outpatient. First consolidation must be administered no earlier than 35-75 days after day 1 of induction. Second and third consolidations will be administered no earlier than 35-56 days after the start of the previous consolidation.
- e. Serum pregnancy test will be performed on females of childbearing potential (FCBP). A FCBP is considered when a sexually mature female: 1) has not undergone a hysterectomy or bilateral oophorectomy; or 2) has not been naturally postmenopausal for at least 12 consecutive months.

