10.3 ANALYSIS DATASETS

- All patients receiving at least one dose of CPX-351 will be evaluable for safety.
- Efficacy analyses will be restricted to those receiving a full cycle of induction therapy.

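### The planned AE table pools induction with up to three consolidations; adding counts by phase would separate the two regimens at the cost of one table

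*Combined protocol and SAP*

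**What the plan says.** Section 10.4.4 summarises AEs "with each AE being counted only once for a given participant". They "will be presented by System Organ Class (SOC) and preferred term groupings". AEs leading to discontinuation, "adverse events of special interest, and serious treatment-emergent AEs will be presented in a table". None of these displays is split by phase or cycle, and the section does not say which grade is kept when an event recurs. Section 10.3 supplies the only safety denominator: "All patients receiving at least one dose of CPX-351 will be evaluable for safety". It defines no set of patients who start consolidation.

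Section 6.1.7 describes two regimens. For induction: "Patients will receive induction with CPX-351 at a dose of 100 u/m² administered intravenously over 90 minutes on days 1, 3 and 5". For consolidation: "This may be followed by consolidation with CPX-351 at a dose of 65 u/m² administered intravenously over 90 minutes on days 1 and 3". Section 6.1.9 allows at most three consolidations. Induction is given in hospital and consolidation to outpatients (section 10.4.5; section 7.3.7, footnote d).

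On collection, footnote c of section 7.3.7 says: "Adverse event data will be captured from the time of consent until 30 days after the last dose of CPX-351". Section 7.1.9 lets collection stop earlier, at the next anti-leukemic therapy, in patients without adequate response. Section 8.3 requires the time of onset of each event. Section 2.2 plans to compare the frequency of myelotoxicity and infection with historical regimens.

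**The concern.** The two phases differ in dose, number of doses and setting, and only some patients reach the second. One count per participant across both gives a figure that describes neither.

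Three things follow. First, a patient counted for a term in induction adds nothing when the same term recurs in consolidation. The protocol expects myelotoxicity and infection, which can recur with each course. Second, an event that first appears in consolidation is counted, but over all treated patients and not over those who could have had it there. Third, the pooled rate depends on how many patients enter consolidation. Entry follows outcome, so a better response rate would by itself raise the AE rate.

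Safety is the first secondary endpoint listed, and the pilot is meant to support a larger study. Two of the historical trials in section 2.2 are described by their induction regimen. A rate pooled over one to four courses is not like-for-like with a rate from an induction. The protocol gives no historical toxicity rates or observation windows that would allow an adjustment.

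**Working it through.** **The plan's own figures.** The plan states no AE rate to reproduce. Its one calculated design, the illustrative Simon two-stage table in section 10.4.2, reproduces: exact binomial sums at 35% and 65% give PET 0.514, average N 14.38, alpha 0.084 and beta 0.095. This point does not rest on that design, but borrows its two response rates below.

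**AE window, in days from the first dose (Day 1), with collection to 30 days after the last dose.**

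- Induction only: last dose Day 5, so 5 + 30 = Day 35, or earlier if new therapy starts.
- Four courses, 28-day minimum intervals (sections 6.1.9, 7.3.2.11 and 7.3.2.14): third consolidation starts Day 1 + 3×28 = 85, last dose Day 87, window ends Day 117.
- Four courses, 35-day minimum intervals (section 7.3.7, footnote d; the study schematic and Appendix A also give 35 days for the first consolidation): start Day 1 + 3×35 = 106, last dose Day 108, window ends Day 138.
- Four courses, longest intervals: start Day 1 + 75 + 56 + 56 = 188, last dose Day 190, window ends Day 220.

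Against Day 35 the ratios are 117/35 = 3.3, 138/35 = 3.9 and 220/35 = 6.3.

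**Dependence on entry to consolidation.** Let pI be the AE probability in induction, pC the probability in each consolidation, k the number of consolidations and q the share of treated patients who enter consolidation. With independence between courses:

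- pooled rate = pI + (1 − pI) × q × [1 − (1 − pC)^k]
- rate within consolidation, among those who start it = 1 − (1 − pC)^k

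pI, pC and independence are assumptions; the documents give no such figures for this population. For q, 35% and 65% are the CR/CRi rates in section 10.4.1. The value 5/6 is the response proportion (CR plus PR) implied by section 2.3.2. Each is used as a stand-in for the share entering consolidation.

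With pI = 30%, pC = 20% and k = 3, the consolidation rate is 1 − 0.8³ = 48.8%, and:

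| q | Pooled rate |
|---|---|
| 35% | 0.30 + 0.70×0.35×0.488 = 42.0% |
| 65% | 0.30 + 0.70×0.65×0.488 = 52.2% |
| 5/6 | 0.30 + 0.70×0.833×0.488 = 58.5% |

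From q = 35% to 65% the shift is 10 points with toxicity unchanged. If each patient has only one consolidation, it is 4 points (34.9% to 39.1%). With k = 3, pI from 10% to 90% and pC from 10% to 30%, the shift is (1 − pI) × 0.30 × [1 − (1 − pC)³]. This runs from 0.1×0.30×0.271 = 0.8 points to 0.9×0.30×0.657 = 17.7 points.

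**Uncounted recurrences.** With pI = 90%, pC = 30% and k = 3, 65.7% of those who start consolidation have the event there. The pooled figure moves only from 90% to 92.3% (q = 35%) or 94.3% (q = 65%).

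**Dilution.** An event seen only in consolidation, in 30% of those who start it, appears as 0.30×0.35 = 10.5% or 0.30×0.65 = 19.5% of all treated.

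**Size of the consolidation denominator.** With 10 patients, q of 35%, 65% and 5/6 gives 3.5, 6.5 and 8.3, so about 4 to 8.

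**The case against.** Counting an event once per participant is the usual incidence convention and stops one patient's repeated events from inflating a rate. A reader might infer that the rule itself is wrong. It is not: the fix keeps it. What is missing is a display by phase beside it. Section 10.4.4 also does not say that the count runs over the whole study. That is the plain reading of a rule with no stated period, and the section does not exclude tables by phase.

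A reader might also infer that consolidation toxicity is hidden altogether. The documents do not support that. Only same-term recurrences in patients already counted drop out. Severity and duration are to be presented, and discontinuation AEs, special-interest AEs and serious AEs are tabulated. Section 8.4.4 times marrow aplasia from the start of induction or consolidation cycles, and calls for cardiac imaging before consolidation above a cumulative exposure. These are monitoring and reporting rules, not an analysis by phase, but they give partial cover. Onset times are collected, so no information is lost.

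A third tempting step is to compare 20% after one course with 1 − 0.8⁴ = 59% after four. That applies one assumed rate to two different regimens and describes only a patient who completes all four courses.

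The strongest objection is the small consequence. All endpoints are exploratory, expansion turns on CR/CRi alone, and no safety threshold uses the pooled rate. With no events among 4 or 6 consolidation patients, the exact two-sided 95% upper limit is 1 − 0.025^(1/4) = 60% or 1 − 0.025^(1/6) = 46%. This stands, and it limits the point to a minor one. It does not remove it, because section 2.2 plans a comparison of AE frequencies with other regimens.

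**Conclusion.** The point holds as a minor improvement. As written, the plan yields one AE rate that cannot separate induction from consolidation and that moves with the share of patients entering consolidation. The direction holds for any AE probabilities strictly between 0 and 1. The size does not come from the documents: the move from 42% to 52% rests on assumed rates, independence, three consolidations for everyone who enters, and CR/CRi rates standing in for entry.

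Two inconsistencies affect these inputs and must be reconciled. Section 6.1.9 admits patients with CR or CRi to consolidation, while sections 7.3.2.11 and 7.3.7 also admit PR and investigator-judged benefit. The earliest start of consolidation is 28 days in some sections and 35 in others. In addition, section 10.4.3 continues safety assessment at least every three months in some patients, so the windows above hold only for the 30-day rule.

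No sample size, error rate or expansion decision changes.

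**What to change.** In section 10.4.4, keep the overall once-per-participant table and add two sets of counts, each once per participant and term at worst grade:

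- AEs with onset from the first induction dose until the first consolidation dose or the end of AE collection; denominator, all treated patients.
- AEs with onset from the first consolidation dose to the end of AE collection; denominator, patients who start consolidation, with the number of cycles received shown.

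In section 10.3, define the set of patients who start consolidation. Use the induction table for the historical comparison in section 2.2 where the historical figure is itself an induction rate.

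The cost is one extra table from onset times already collected. The downside is a consolidation denominator of about 4 to 8 patients, so that part should be labelled descriptive.
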